### **- Randomization and intervention procedure**

All the volunteers that will meet the inclusion criteria will sign the informed consent before the study started. The volunteers will randomly allocate in control or intervention group (1:1 allocation ratio to each group) in blocks of 2 by using Microsoft Office Excell. Nobody involved with data acquisition will have access to de assignment of the subjects. Once randomly assigned, a blood sample and anthropometric variables will take to establish basal data. Participants will interview to know, caloric intake (24-h food recall), consumed portions and beverage consumption (Food frequency questionnaire). The intervention group is not allowed to consume ASBs, however they are allow consuming products that did not contain ASs in their formulae. For the control group ASBs consumption are not modified. Both groups continue the normal food habits.

Anthropometric measures, 24-h food recall and food frequency questionnaire data will collect at week 6 and 12. Blood sample will take once more at study week 12. In order to categorize the physical activity a previously validated questionnaire will apply, the physical level are divide in low, moderate and high.

- **Study population**

Young overweight or obese students between 19 and 27 years old with normally consumption of ASBs

- **Sample**

It is a probabilistic, stratified sampling that is made from the overweight and obese population who consume ASBs.

The data for obtaining the sample will be collected from the questionnaires that will be applied to the students in which we will know who consume ASBs.

- **Statistic**

They will be analyzed with the statistical program SPSS 21. With a two-way analysis of variance ANOVA or T-student test with repeated measures. And the variables will be correlated.

- **Ethical and biosecurity considerations**

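### Overweight or obesity is required for entry, but the first measurement described that could confirm it is taken after random assignment

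*Protocol*

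**What the plan says.** Under Study population, the protocol defines who may enter: "Young overweight or obese students between 19 and 27 years old with normally consumption of ASBs". Under Sample, it says of the source of participants: "It is a probabilistic, stratified sampling that is made from the overweight and obese population who consume ASBs". The sampling data are to be "collected from the questionnaires that will be applied to the students in which we will know who consume ASBs".

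The Randomization and intervention procedure section gives the order of events. It opens with eligibility and consent: "All the volunteers that will meet the inclusion criteria will sign the informed consent before the study started". Allocation follows, 1:1 in blocks of 2. Then comes the basal visit: "Once randomly assigned, a blood sample and anthropometric variables will take to establish basal data". Later body measurements are scheduled as follows: "Anthropometric measures, 24-h food recall and food frequency questionnaire data will collect at week 6 and 12".

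On access to the allocation, the same section states: "Nobody involved with data acquisition will have access to de assignment of the subjects".

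The Hypothesis section expects the restriction to lower both anthropometric values and biochemical markers, so anthropometry is an outcome as well as the natural check of the entry criterion.

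**The concern.** An entry criterion based on body size needs a body measurement before allocation. Here the protocol treats weight status as known when students are allocated, yet the first measurement it describes that could establish it falls after allocation. Two things are at stake.

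- **Who is randomised.** If the basal visit shows that a student is not overweight, that student already has an arm. Keeping the student moves the trial away from the population named in the Objective. Removing the student is an exclusion after randomisation. Measuring first avoids the choice.
- **What the baseline represents.** A basal value of an outcome should be fixed before assignment can influence it. The intervention arm is told to stop drinking ASBs, so participants cannot follow the protocol without learning their arm. The protocol does not say whether they learn it before or after the basal visit, nor how long after assignment that visit takes place. If behaviour changes in that interval, part of any effect is absorbed into the baseline and the change from baseline is understated.

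**Working it through.** No arithmetic applies. The protocol states no figure on this point, and none of the inputs needed to compute one. The check is to find every place where weight status could be established and set it against the moment of allocation.

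1. **Study population.** Overweight or obesity is required. No BMI value or other cut-off is given, and no method of measurement.
2. **Sample.** The source population is described as already overweight or obese. How that is known is not said. The questionnaire is credited with identifying ASB consumers. It is not said to record weight, height or BMI.
3. **Ethical and biosecurity considerations.** The questionnaire is applied in classrooms, and the consent letter is delivered before it. The procedure section instead links consent to having met the inclusion criteria. Whichever order is followed, neither section describes a body measurement at this stage.
4. **Randomization and intervention procedure, allocation.** Students who meet the criteria are allocated.
5. **Same section, basal visit.** Blood and anthropometry are taken once the student is assigned. The stated purpose is to establish basal data, not to check eligibility.
6. **Same section, follow-up.** Anthropometry is repeated at weeks 6 and 12, also after assignment.
7. **Ethical and biosecurity considerations, after the study.** Anthropometry is mentioned once more, as the basis of a personal nutritional plan in the 3 months after the study ends. This is not screening.

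Items 5 to 7 are the only mentions of anthropometric measurement in the plan's procedures, and all fall after allocation. Items 1 and 2 need weight status to be known before allocation. The protocol therefore declares the criterion met at a point where nothing it describes has measured it.

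For the baseline, item 5 together with the Hypothesis is enough: a basal outcome measurement is explicitly placed after assignment. The basal blood sample is placed in the same sentence, so the argument about baseline timing applies to it too, although the entry check needs only height and weight.

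**The case against.** The strongest reply is that the protocol says inclusion criteria are met before allocation and draws its sample from people already overweight or obese. On that reading weight status is established earlier by a method not written down, and the later anthropometry is simply the baseline. There is also contact with each student in the classroom, when a weighing could take place. This stands in part: the protocol does not say that eligibility is decided after assignment. It does not remove the point, because the order is stated and not merely left open. A specific instrument is named and credited with beverage use alone, and the first described body measurement is explicitly placed after assignment.

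The second reply is that data collectors have no access to the assignment. This also stands, and it limits the harm. Exclusion on measured basal body size by staff unaware of the arm would not be expected to differ between arms, as long as the measurement precedes any effect of the arm. It does not protect the baseline from changes made by participants who already know their arm.

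A reader might infer more than this. Four stronger readings are not supported:

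- *Weight status is judged by self-report or by appearance.* Neither is mentioned anywhere in the protocol.
- *Ineligible students are removed in a way that depends on their arm.* No removal after randomisation is described, participants do not decide exclusions, and data collectors lack the assignment.
- *Losing one member of a block of 2 damages the analysis.* The Statistic section plans a two-way ANOVA or a repeated-measures t test and does not mention matching by block. The result would be a small imbalance in numbers.
- *A given percentage of entrants would be ineligible.* Any such figure would rest wholly on assumed BMI distributions and reporting errors for a process that the protocol does not describe.

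**Conclusion.** The point holds in a limited form. Overweight or obesity is an entry criterion, no measurement described before allocation confirms it, and the first anthropometry described follows assignment. A student later found not to be overweight could therefore already have been randomised, and an outcome baseline is taken after the arm is assigned.

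The size is unknown, and the documents do not allow a range. The entry problem is nil if an undescribed weighing takes place before allocation. The baseline problem is likely to be slight if the basal visit follows assignment immediately or if participants learn their arm only afterwards; the protocol settles neither. The conclusion rests on the text alone, plus one assumption: that the unlisted basal anthropometric variables include height and weight.

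The missing cut-off and the absence of a rule for participants found ineligible would, taken alone, be missing detail, and the second may be covered in a statistical analysis plan that is not at hand. The flaw is the stated order. It calls for a cheap improvement and does not show that the randomised comparison is broken.

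**What to change.** Change the order in the Randomization and intervention procedure section:

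1. After consent and before allocation, take the basal height and weight already planned.
2. Randomise only students whose overweight or obesity is confirmed by that measurement against the definition stated in the protocol. The definition has to be written into Study population for this step to work.
3. Use the same measurement as the basal value for the analysis.
4. Keep everyone who is randomised in the comparison, whatever later measurements show.

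This adds no new procedure. The cost is that a few students are measured who are then not randomised. In return, the entry criterion is confirmed before allocation and the baseline of an outcome is fixed before the arm is assigned.

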**February, 2018**

## Introduction

Overweight and obesity are public health problems across the world. In 2016 the World Health Organization (WHO) estimated that over 1900 million adults were diagnosed as overweight or obese (1). Currently, these pathologies are associated with the risk of developing pathologies such as insulin resistance, Type 2 Diabetes Mellitus(T2DM) and Metabolic Syndrome (2).

These pathologies result from the interaction between many factors, mainly poor alimentary habits and a sedentary lifestyle (2-4). The high consumption of simple carbohydrates and sugar sweetened beverages (SSBs), like soft drinks, juices and flavored water, is considered one of the main factors that contribute to the increase in incidence and prevalence of overweight and obesity. A high consumption of simple carbohydrates promotes an increase glucose concentrations in blood, which facilitates the formation of triglycerides that are subsequently stored in adipose tissue (2, 4, 5).

Mexico is the Latin American country with the highest consumption of SSBs. It was estimated that the intake per person was 384 SSBs per year (6). The exact figures of the population that consumes ASBs are not known. However, an increase in the consumption of products containing artificial sweeteners (ASs) was reported (7, 8). In Mexico, more than 70% of the adult population has been diagnosed as overweight or obese (1).

To decrease the caloric intake attributable to SSBs, the food industry promotes the commercialization of ASBs (9). These products have the same organoleptic features than SSBs, with the perks of having a minimum or no caloric contribution at all, not

affecting the energy metabolism (10). For this reason, in Mexico the official treatment guidelines for overweight and obesity recommend its use as part of the nutritional treatment (11).

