Nonetheless, recent studies relate the consumption of ASBs with a deregulation of the metabolic homeostasis, promoting physiological modifications (12). In a study conducted by Duran, *et. al.* aiming to evaluate the effect of the reduction of SSBs and ASBs, concluded that the reduction in the consumption of these beverages decreased weight and body fat (13). On the other hand, Madjad, *et. al.* reported a decrease in body weight of women with type 2 diabetes mellitus after substituting the consumption of ASBs, for water (14). Some cohort studies reported an association between the consumption of ASBs and the increase in body weight and waist circumference (4, 15). Likewise, it was reported that ASs increased glucose and insulin concentrations in blood, which is detrimental to health, especially in population with a pre-existing risk of developing non-infectious diseases, such as overweight and obesity (12, 16-18).

While population increases the consumption of ASBs, the prevalence of overweight and obesity increased too. To contribute to the knowledge on the effect of these substances in the human body, we evaluated the effect of reducing the consumption of ASBs in overweight and obese young adults.

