## **Design and methods**

### **- Study Design**

This study is a single-blind randomized clinical trial it will perform at the University of Veracruz, Veracruz, Mexico, between February 2017 to October 2018. Young adults students of the University of Veracruz will randomly allocate to a 12-week no consumption of ASBs intervention or control group.

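### Does allowing products without artificial sweeteners contradict the instruction to keep usual eating, and so leave the intervention and adherence undefined?

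*Protocol*

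**What the plan says.** Study Design sets the contrast as a "12-week no consumption of ASBs intervention or control group". The Objective and the Hypothesis speak of restricting ASBs and name no other drink or food.

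Randomization and intervention procedure gives three rules for intake:

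- Intervention arm: "The intervention group is not allowed to consume ASBs, however they are allow consuming products that did not contain ASs in their formulae".
- Control arm: ASB intake is left as it is.
- Both arms: "Both groups continue the normal food habits".

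The same section provides for measurement. The baseline interview covers caloric intake by 24-hour recall and "consumed portions and beverage consumption (Food frequency questionnaire"). During follow-up, "24-h food recall and food frequency questionnaire data will collect at week 6 and 12".

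The protocol does not name a substitute for ASBs and sets no limit on one.

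**The concern.** The ban is framed by type of drink, the permission by ingredient. A sugar-sweetened drink without artificial sweeteners falls within the permission, yet drinking more of it than before is hard to call keeping to usual habits. The permission can also be read as excluding solid foods that contain artificial sweeteners, which the ban on beverages does not mention.

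The protocol's own background gives the first point weight. The Introduction counts "The high consumption of simple carbohydrates and sugar sweetened beverages (SSBs), like soft drinks, juices and flavored water" among the main contributors to overweight and obesity, and adds: "A high consumption of simple carbohydrates promotes an increase glucose concentrations in blood". The Hypothesis predicts falls in anthropometric and biochemical measures. Of the two beverage trials cited in support, one is described as "aiming to evaluate the effect of the reduction of SSBs and ASBs" and the other replaced ASBs with water. Neither is described as removing ASBs while leaving SSB intake free to rise.

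If the instruction were truly contradictory, participants might be told different things, the same questionnaire answer might count as adherence or departure, and the intervention would be hard to repeat.

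**Working it through.** The protocol gives no sample size, expected effect, ASB servings or replacement rate, so there is no figure to reproduce. The check is of the text, followed by what substitution would do to the comparison.

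**1. Behaviour in the intervention arm against each rule**

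| Behaviour | Ban on ASBs | Permission for products without sweeteners | Usual habits |
|---|---|---|---|
| ASBs replaced by water | met | met | can be met |
| ASBs dropped, SSBs as before | met | met | met |
| ASBs dropped, SSBs increased | met | met | depends on the reading |
| ASBs dropped, usual foods with sweeteners kept | met | outside its literal wording | met |
| ASBs still drunk | broken | broken | met |

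The ban classifies every row. Only the third and fourth rows are open, and neither concerns the factor under test.

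**2. Are the sentences incompatible?** The first is a ban with a permission attached, and a permission directs nobody to drink more sugar. The last is a general statement for both arms. It must already carry an exception, because the trial recruits people who normally drink ASBs, and stopping them is itself a change of habit. A specific rule followed by a general statement that all else goes on as usual is a common construction: remove ASBs, prescribe nothing further.

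**3. What does substitution do to the comparison?** Let *d* be the effect of removing ASBs with other intake held fixed, *p* the mean extra SSB intake that removal brings about, and *s* the effect per unit of that intake. Taking these effects as additive for illustration:

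arm difference = *d* + *p* × *s*

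The documents give none of these values and none is assumed. For any *p*, the comparison of the randomised arms is unbiased for the sum, because *p* arises after allocation and as a result of it. The Objective asks for the effect of restricting ASBs and sets no condition on other drinks, so the sum is the quantity asked for. A large *p* × *s* could offset *d*. That would be a real property of the restriction as delivered.

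**4. Could a reader tell?** Beverage intake is recorded at baseline, week 6 and week 12, so a rise in SSBs in one arm can be described. Follow-up lasts 12 × 7 = 84 days. If each recall covers one day, the two follow-up recalls cover 2 / 84 = 2.4% of it. Beverages are assigned to the food frequency questionnaire, however, so this percentage does not measure how well substitution is seen.

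**5. Would counting readings give a size?** Two open points (may SSB intake rise; are foods with sweeteners covered) allow 2 × 2 = 4 readings, or 2 if the Objective, Hypothesis and Study Design settle the second point in favour of beverages only. A count of readings is not an effect on any result.

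**6. What would rewriting now bring?** The document is dated February 2018, and the study runs from February 2017 to October 2018. About 12 of 20 months had passed. If enrolment was open throughout, which the protocol does not state, new wording would reach only later entrants and could itself put two versions of the instruction in one arm.

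**The case for a change.** The strongest case for a change is that what participants are told is the intervention itself. It belongs in the protocol and cannot be left to an analysis plan. Reading the last sentence as covering food but not drink is also not secure, since the protocol records beverages with a food frequency questionnaire. Even on that reading the substitute is unspecified, and the Introduction treats SSBs as harmful to the very outcomes being measured.

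Much of this stands. The protocol is silent on substitutes, and a more explicit instruction would make the trial easier to repeat. A null result would also be harder to interpret if SSB intake rose in the restricted arm.

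Two steps do not stand. Silence on substitutes is not a contradiction, since the sentences can all be followed together. Nor is adherence to the tested factor undefined: either ASBs were drunk or they were not. How other questionnaire answers are coded for analysis is commonly settled in an analysis plan, which is not at hand. The fear that participants receive opposite instructions is conjecture. The section on ethical considerations makes the main researcher responsible for explaining the procedures to participants. That does not settle the SSB question, but it makes conflicting advice less likely.

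**Conclusion.** No change to the plan is needed. The wording is loose, but the rule under test is fixed and consistent across sections, the randomised comparison validly estimates the effect of restricting ASBs, and the intake data needed to describe substitution are already collected. What remains is a minor gap in describing the intervention, of a kind investigators can fill sensibly when they instruct participants and report intake by arm. Which dietary rule should apply is their decision, and this review takes no position on it.

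The conclusion rests on two assumptions: that the arms are compared as allocated, without adjusting for drink intake after allocation, and that findings are stated as effects of ASB restriction, as the Objective words them. It would differ if the trial claimed the effect of removing ASBs with SSB intake held constant; the protocol makes no such claim.

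### The Statistic paragraph permits, as an alternative to the ANOVA, a t-test that is ordinarily a within-arm paired test; the between-arm difference should be fixed as the treatment effect

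*Protocol*

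**What the plan says.** The protocol describes a parallel randomised trial in which students "will randomly allocate to a 12-week no consumption of ASBs intervention or control group", in a 1:1 ratio. The control condition is plain: "For the control group ASBs consumption are not modified".

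The outcomes are measured on different schedules. Anthropometry is taken at baseline and then twice more: "Anthropometric measures, 24-h food recall and food frequency questionnaire data will collect at week 6 and 12". Blood is drawn at baseline and then "Blood sample will take once more at study week 12". So the blood markers have two occasions and the anthropometric measures three.

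The Statistic paragraph names SPSS 21 and then gives the tests: "With a two-way analysis of variance ANOVA or T-student test with repeated measures". It adds "And the variables will be correlated", which is not a treatment comparison. The protocol does not state the ANOVA factors, the contrast to be tested, or which of the two methods applies to which outcome.

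**The concern.** A Student t-test described as being for repeated measures ordinarily means the paired t-test: the same people, two occasions, one arm. It asks whether that arm changed over time. It does not ask whether the intervention arm changed more than the control arm, which is the question the randomisation was set up to answer.

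The two methods are joined by *or* without a rule, so the sentence as written would allow the paired test to carry a conclusion by itself. Any change common to both arms over 12 weeks could then be credited to the restriction. Its source could be the season, the academic term, being measured, or regression to the mean. A comparison of the arms cancels such a change using data the trial already plans to collect.

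**Working it through.** The protocol states no sample size, alpha, SD or expected change, so there is no figure of its own to reproduce. The check has three steps.

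**1. Which listed test compares the arms?**

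| Option | What it tests | Uses the control arm? |
|---|---|---|
| Two-way ANOVA, arm and time as factors, interaction tested | Difference between arms in change over time | Yes |
| Paired t-test (ordinary reading) | Change over time within one arm | No |
| Unpaired t-test on change scores (possible reading) | Difference between arms in change | Yes |

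With two occasions (the blood markers) the arm by time interaction is the same test as the unpaired t-test on change. With three occasions (anthropometry) it has (2 − 1) × (3 − 1) = 2 degrees of freedom, so it is an omnibus test and not a week-12 difference.

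**2. What could happen if conclusions rested on paired tests?**

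Assumptions, none of them from the protocol: no treatment effect; the same true decrease *d* in both arms, in baseline SD; baseline to week-12 correlation ρ; equal SDs; *n* per arm; two-sided alpha 0.05.

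- SD of change = √(2(1 − ρ)).
- Noncentrality of the paired test = d√n / √(2(1 − ρ)), with n − 1 degrees of freedom.
- q = probability of a significant decrease in one arm.
- The arms are independent, so P(significant decrease in the intervention arm and not in control) = q(1 − q).

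With d = 0: q = 0.025 and the rate is 0.025 × 0.975 = 0.024.

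Example with d = 0.1, n = 30, ρ = 0.8: noncentrality = 0.1 × √30 / √0.4 = 0.866; q = 0.131; rate = 0.131 × 0.869 = 0.114.

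Rates at d = 0.1:

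| n per arm | ρ = 0.5 | ρ = 0.8 | ρ = 0.95 |
|---|---|---|---|
| 15 | 5% | 8% | 16% |
| 30 | 7% | 11% | 24% |
| 60 | 10% | 17% | 22% |

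The drift at which the rate reaches 5%, about double its no-drift value, is:

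| n per arm | ρ = 0.5 | ρ = 0.8 | ρ = 0.95 |
|---|---|---|---|
| 15 | 0.094 SD | 0.060 SD | 0.030 SD |
| 30 | 0.064 SD | 0.041 SD | 0.020 SD |
| 60 | 0.045 SD | 0.028 SD | 0.014 SD |

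The rate cannot exceed 25%, the maximum of q(1 − q) at q = 0.5. It falls again when the drift is large enough to show in both arms: 0.1% with n = 30, ρ = 0.95, d = 0.3.

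**3. What does a between-arm test do in the same cases?**

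In simulation (20,000 trials in each of 36 combinations of n, ρ and drift from 0 to 0.3 SD), two-sided rejection was 4.7% to 5.1% for the change-score test and 4.6% to 5.3% for ANCOVA. The rates in step 2 count decreases only, so the like-for-like benchmark is half of 5%, about 2.5%.

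For the two-occasion ANOVA, leaving out baseline adjustment costs efficiency only. The extra participants needed relative to ANCOVA are 2/(1 + ρ) − 1, which is 33%, 11% and 3% at ρ = 0.5, 0.8 and 0.95.

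**The case against.** Four arguments on the other side deserve weight.

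- **The sentence is loosely worded.** The reference to repeated measures can attach to both tests. The first-named method is then a repeated-measures ANOVA, whose natural factors in this design are arm and time. The t-test might be an unpaired test on change, or a follow-up to the ANOVA. This stands: the paired reading is likely, not certain.
- **Nothing says a conclusion will rest on the paired test alone.** A reader might infer that the trial plans no comparison with control, and might cite the Hypothesis, which is worded as a decrease under restriction. The protocol does not support that. It randomises against an unmodified control arm, and its first-listed method can make the comparison. The sentence permits a within-arm conclusion; it does not plan one.
- **Naming contrasts is usually work for the SAP.** That holds for much of the detail, and a SAP may exist. It does not dispose of the point, because the protocol itself offers, as an alternative, a test that on its ordinary reading ignores the control arm.
- **The size is wholly assumed.** Sample size, correlation and drift are not in the protocol. It predicts no shared drift, and it has both arms keep their usual eating habits. This stands: the percentages are illustrations, and reading 24% as this trial's false-positive rate would be wrong.

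A reader might also take the ANOVA to be wrong because it does not adjust for baseline. It is not; adjustment makes it more efficient and corrects no error.

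**Conclusion.** The point holds in conditional form. One of the two permitted analyses is, on its ordinary reading, a within-arm test, and the protocol has no rule that prevents a conclusion from resting on it. If one did, and if both arms shared a modest drift, the chance of an apparent effect in the intervention arm only would rise from 2.4% to between 5% and 24% over the assumed range (15 to 60 per arm, correlation 0.5 to 0.95, drift 0.1 SD). The between-arm benchmark in the same direction is about 2.5%. With no drift there is no inflation. If the t-test meant is unpaired on change scores, or if the ANOVA interaction carries the conclusion, the concern reduces to unclear wording. Confidence is medium because the reading is uncertain, but the sentence should be corrected, since it leaves open which contrast is the treatment effect.

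**What to change.** Replace the sentence on tests with a statement to this effect: the treatment effect is the between-arm difference at week 12, adjusted for the baseline value. For the blood markers it is estimated by ANCOVA. For the anthropometric measures it is estimated by a repeated-measures model with baseline, arm, visit and arm by visit, read at week 12. Within-arm paired t-tests are descriptive only.

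If the ANOVA is kept, name arm and time as its factors and the arm by time interaction as the test. For anthropometry, add the week-12 between-arm contrast, because the interaction over three occasions does not by itself answer the week-12 question.

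The cost is low: a few lines of text, no extra data, and models that SPSS 21 can run. Timing needs care. The protocol is dated "February, 2018", while the stated study period runs "between February 2017 to October 2018", so the document's date falls 12 months after the stated start. The change should therefore be a dated amendment, with a statement that it was made without sight of outcome data by arm.
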